4.7. Safety Variables

Patient safety will be assessed through the collection of reported adverse events (AEs), clinical laboratory data, and vital signs. Unless otherwise noted, the baseline value is defined as the last available value before the first dose study treatment.

4.7.1. Adverse Events Variables

The period of safety observation starts from the time when the patient gives informed consent and continues into the following periods:

- The PRE-TREATMENT period: defined as the time from the signed informed consent up to the first study treatment injection.
- The treatment-emergent adverse event (TEAE) period: defined as the time from the first study treatment injection up to the day of the last study treatment injection + 70 days (10 weeks), as residual effect of Praluent is expected until 10 weeks after last dose of study treatment.

The TEAE period will include:

- The TREATMENT period is defined as the time from the first study treatment injection up to the day of last study treatment injection + 21 days, as serum concentration of alirocumab >10 µg/mL is expected for approximately 21 days following administration of 150 mg. Further, in previous studies, alirocumab concentrations declining below this concentration also showed a decrease in effect on LDL-C.
- The RESIDUAL TREATMENT period is defined as the time from the day of last study treatment injection + 22 days up to the day of last study treatment injection + 70 days (10 weeks).
- The POST-TREATMENT period: defined as starting the day after the end of the TEAE periods (i.e., 71 days after the last study treatment injection) up to the patient's end of study.

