5.7.2. Prohibited Medications

Commercially-available PCSK9 antibodies are prohibited from the initial screening visit until the end of the study visit.

Sleep-aid medications are prohibited the night before the baseline visit, or the week 24, week 48, week 72, or week 96 visits. If the patient used such medication, the visit should be rescheduled as soon as possible.

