Research samples (serum and plasma)			X			X		X				X	
			X										

ADA = anti-drug antibody, CPK = creatine phosphokinase, EOS = end of study, F/U = follow-up, HbA1c = hemoglobin A1c, hs-CRP = high-sensitivity

C-reactive protein, S = serum, TSH = thyroid-stimulating hormone, U = urine, WOCBP = women of childbearing potential

- Visit 2 is optional.
- Injection training will be performed with the patient and/or caregiver at visit 2, at visit 3, or at visits 2 and 3 using placebo. Refer to Section 5.1 for additional information on injection training.
- The patient or caregiver will administer the first dose of double-blind study drug in the clinic on day 1. The patient will be monitored for 30 minutes after the first dose. Subsequent doses of study drug must be administered Q2W. Study drug will be administered at home between week 84 and week 94. The last dose of study drug will be administered at home at week 94. Patients will come into the clinic for the last study visit at week 96.
- Injection supplies and the dosing log will be provided to the patient.
- See Appendix 6 for diet.
- Menstrual cycle data will be collected for women of childbearing potential who are not on hormonal contraceptives.

7. On days when a clinic visit coincides with a dosing day (visits 3, and 8), blood samples (including ADA samples) will be collected after study assessments are performed and before the dose of study drug is administered. At visits 4, 5, 6, 7, 9, 10, and 11, study drug may be administered prior to study assessments.
8. If a neurocognitive AE is reported during the visits when the test is not planned or in case of early treatment discontinuation, an unscheduled neurocognitive battery test will be performed.
9. Samples will be tested for Total-C, calculated LDL-C, HDL-C, TG, and non-HDL-C, Apo B, Apo A-1, Apo B/Apo A-1 ratio, and Lp(a).
10. For female patients – estradiol, follicle-stimulating hormone (FSH) and luteinizing hormone (LH); for male patients – testosterone, FSH and LH.
11. Dipstick and, if abnormal, microscopy.

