8.2. Recording and Reporting Adverse Events

All SAEs, regardless of assessment of causal relationship to study drug must be reported to the sponsor (or designee) as follows:

- Telephone the sponsor (or designee) at the contact information provided in the SAE completion guidelines, within 24 hours of learning of the event
- Complete the SAE form utilizing the AE e-CRF in the electronic data capture (EDC) system and submit within 24 hours of learning of the event

The sponsor (or designee) will provide the investigators with blank SAE forms, which are to be completed in the event that access to the EDC system is not available. Once the EDC system is available, the SAE information must be entered within 24 hours of the system availability. Information not available at the time of the initial report must be documented in the EDC within 24 hours of receipt of the new information. Substantiating data such as relevant hospital or medical records and diagnostic test reports may also be requested.

The investigator must promptly report to the Institutional Review Board (IRB)/Ethics Committee (EC) all unanticipated problems involving risks to patients. This includes death from any cause and all SAEs related to the use of the study drug. It is recommended that all SAEs be reported to the IRB/EC, regardless of assessed causality.

In the event the investigator is informed of an SAE after the patient completes the study, the following will apply:

- SAE with an onset within 30 days of the end of study/early termination visit - the SAE will be reported to the sponsor. The investigator should make every effort to obtain follow-up information on the outcome until the event is considered chronic and/or stable.
- SAE with an onset day greater than 30 days from the end of study/early termination visit - only fatal SAEs and those deemed by the investigator to be drug-related SAEs will be reported to the sponsor. The investigator should make every effort to obtain follow-up information on the outcome of a drug-related SAE until the event is considered chronic and/or stable.

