8.2.1. Deaths

Any AE that results in death is considered an SAE. Deaths that occur from the time the patient signs the ICF until 70 days after dosing must be reported to the appropriate IRB/EC and to Regeneron Pharmacovigilance and Risk Management (or designee) within 24 hours of learning of the death. The reporting procedures detailed in Section 8.2 should be followed.

Any available autopsy reports and relevant medical reports must be sent to the sponsor (or designee) as soon as possible.

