9.5.2.6. Adverse Events

All AEs reported in this study will be coded using the currently available version of the Medical Dictionary for Regulatory Activities (MedDRA®). The verbatim text, the preferred term (PT), and the system organ class (SOC) will be provided in patient listings.

Definitions

For safety variables, the following observation periods are defined:

- The pretreatment period is defined as the time from signing the ICF to before the first dose of study treatment.
- The TEAE period is defined as the time from the first dose of study treatment to the last dose of study treatment + 70 days (10 weeks) (residual effect of treatment is expected until 10 weeks after the last dose of study drug).
- The post-treatment observation period is defined as the time from the day after the end of the TEAE period up to the last study visit.

Pretreatment AEs are defined as those that developed, worsened, or became serious during the pretreatment period.

Treatment-emergent adverse events are defined as those that developed, worsened, or became serious during the TEAE period.

Post-treatment AEs are defined as those that developed, worsened, or became serious during the post-treatment period.

Analysis

Adverse event incidence tables will be presented by (at least) SOCs sorted by internationally agreed order, and PTs sorted by decreasing frequency in the Praluent group. The number (n) and percentage (%) of patients experiencing an AE will be shown. The high level group term and high level term can be added in alphabetical order, as applicable. Multiple occurrences of the same event in the same patient will be counted only once in the tables within a treatment phase. Data conventions for missing or partial AE dates will be addressed in the SAP. The denominator for computation of percentages is the safety population within each treatment group.

Adverse event incidence tables will be provided by treatment group for all types of TEAEs: all TEAEs, all TEAEs of interest (defined with a PT or a prespecified grouping), TEAE by severity, all treatment-emergent SAEs, and all TEAEs leading to permanent treatment discontinuation.

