4.4. Patient Disposition

Patient disposition includes the description of patient status at major milestone decisions in the study, as well as the patient analysis populations.

For patient study status, the following milestone categories are defined below. For all categories of patients, percentages will be calculated using the number of randomized patients as the denominator, with two exceptions. Specifically, the two exceptions are for the screened and non-randomized categories, which will not have associated percentages shown.

- Screened patients: The total patient counts will only be shown for pre-randomization information, and percentages will not be provided
- Screen failure patients and reasons for screen failure: The total patient counts will only be shown for pre-randomization information. Non-randomized but treated patients (include if applicable): The total patient counts will only be shown for pre-randomization information, and percentages will not be provided
- Randomized patients
- Randomized but not treated patients and reason for not being treated (including patient's decision for treatment period discontinuation)
- Randomized and treated patients
- Patients complete 96 weeks of double-blind treatment period (at least 94 weeks of exposure and visit W96 performed)
- Patients completed the study treatment period (i.e. as collected on the End of Double Blind Treatment eCRF)
- Patients who did not complete the study treatment period and patient's decision for treatment period discontinuation (as per the End of Double Blind Treatment eCRF)
- Patients who discontinued study treatment by main reason for permanent treatment discontinuation (as per the End of Double Blind Treatment eCRF)
- Patients completed the study (i.e. as collected on the Study Completion eCRF)
- Patients who early terminated the study (as per the Study Completion eCRF)
- Patients who early terminated the study by main reason for early termination (as per the Study Completion eCRF)
- Patients who will participate in the Open Label Extension Study
- Status at last study contact

As defined in Section 3. of this document, the patient analysis populations are:

- Randomized population
- Safety Population (SAF)
- Primary Safety Population (PSAF)

- Intent-to-Treat Population (ITT)
- Modified Intent-to-Treat Population (mITT)
- The Anti-alirocumab Antibody Population (ADA)

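### The 70-day TEAE tail does not stop when a patient starts extension drug or another PCSK9 inhibitor, so a serious event or death on newly started active drug can be tabulated under placebo

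*SAP*

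**What the plan says.** The end of the TEAE period is fixed by the last injection alone. SAP 4.7.1 sets it "up to the day of the last study treatment injection + 70 days (10 weeks"), and Protocol 9.5.2.6 uses the same rule: "the first dose of study treatment to the last dose of study treatment + 70 days (10 weeks"). The SAP's reason is that residual drug effect is expected for ten weeks.

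The footnotes to the schedule of events (Protocol 7.1) fix the calendar: "The last dose of study drug will be administered at home at week 94" and "Patients will come into the clinic for the last study visit at week 96".

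Protocol 5.7.2 restricts other drugs of the class only up to that visit; commercial "PCSK9 antibodies are prohibited from the initial screening visit until the end of the study visit". SAP 4.4 lists a disposition category for what may follow: "Patients who will participate in the Open Label Extension Study".

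Reporting continues after the visit. Protocol 8.2 requires reporting of any "SAE with an onset within 30 days of the end of study/early termination visit", and after that of fatal or drug-related SAEs only. Protocol 8.2.1 adds: "Deaths that occur from the time the patient signs the ICF until 70 days after dosing must be reported".

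SAP 4.7.1.3 classes any death in the TEAE period as on-treatment. SAP 5.7.1 uses the end of the TEAE period for Kaplan-Meier censoring, and its full length as patient-years for a patient without an event. SAP 3.1.1 assigns patients by study treatment received. The one mixed-exposure rule (SAP 3.1.2) moves a patient to Praluent only for blinded study drug from more than one arm during the trial.

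**The concern.** The tail is there to catch residual effects of the blinded treatment. Once a patient starts a PCSK9 inhibitor after the last visit, the remaining days no longer measure that. A Praluent patient who continues stays on the class. A placebo patient changes exposure but keeps the placebo label, and nothing in either document separates the two situations.

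Elsewhere the SAP does respect exposure when attributing events: its exploratory analysis by up-titration status (SAP 5.7) treats the period before week 12 separately, because only the lower dose was in use then. There is no counterpart at the end of treatment.

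What is at stake is the descriptive comparison of serious events and deaths. Safety is a study objective, and these events may be few enough for a handful of misattributed cases to be visible. If the class causes a given harm, placing such events under placebo narrows the difference between arms.

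**Working it through.** **Inputs.** Last injection at week 94; last visit at week 96, window ±7 days (Protocol Table 1); TEAE tail of 70 days (SAP 4.7.1); SAE reporting for 30 days after the visit (Protocol 8.2); 651 evaluable patients per arm (Protocol 9.2), used only to illustrate size.

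**Calendar for an on-schedule completer.**
- The tail as stated: 70/7 = 10 weeks, which agrees with the SAP.
- Last injection: 1 + 94×7 = day 659.
- Last visit: 1 + 96×7 = day 673, which agrees with Table 1.
- End of TEAE period: 659 + 70 = day 729.
- Tail after the visit: 729 − 673 = 56 days; with the window, 729 − 680 = 49 to 729 − 666 = 63.
- Share of the completer's TEAE time: 56/729 = 7.7%.

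**What is reportable in those 56 days.**

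| Days | Length | Reportable |
|---|---|---|
| 674–703 | 30 | all SAEs and deaths |
| 704–729 | 26 | fatal or drug-related SAEs, and deaths |

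The 30 days are 30/729 = 4.1% of the TEAE time. Non-serious events are outside the problem: routine AE collection stops at the last visit (Protocol 7.6.4.4 and 8.2.5).

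**Early leavers.** Protocol 7.4.1 asks for the final visit within 5 days of stopping, if possible. If that visit falls 5 days after the last injection, 70 − 5 = 65 days of tail remain. A patient who stops drug but stays in the study remains under the ban.

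**Search for a stopping rule.** The TEAE definitions in Protocol 6.2.1, 9.3.1.2 and 9.5.2.6 and in SAP 3.1.2, 4.6.1 and 4.7.1 all end at last injection + 70 days, with no exception. The censoring and patient-year rules in SAP 5.7.1 inherit that date.

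**Illustrative size.** Uptake and event rates are assumptions; neither is in the documents. Suppose a fraction u of 651 placebo completers start a PCSK9 inhibitor at day 673.
- Active-drug time in the placebo TEAE period: 651 × u × 56/365.25 = 10 patient-years at u = 10% and 100 at u = 100%.
- Part with all SAEs reportable: 651 × u × 30/365.25 = 5 to 53 patient-years.
- At 5 to 15 SAEs per 100 patient-years in that part: 5.3 × 0.05 = 0.3 to 53.5 × 0.15 = 8 SAEs.
- At 0.5 to 2 deaths per 100 patient-years over the whole tail: 10.0 × 0.005 = 0.05 to 99.8 × 0.02 = 2 deaths.

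For comparison, 651 completers contribute 651 × 729/365.25 = 1,299 patient-years of TEAE time.

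**The case against.** **Direction.** A reader might infer that the rule always makes Praluent look safer. The documents do not support that. The same tail applies to Praluent patients, whose later events count as Praluent TEAEs. Crossover time also enters the placebo denominator, and an event that the class prevents would be biased the other way. What stands is dilution for harms that the class causes.

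**Data flow.** Protocol 8.2 covers SAEs of which the investigator is informed after completion, and Protocol 8.2.1 sends deaths to the ethics committee and pharmacovigilance. SAP 4.7.1.1 records AEs until the end of study without saying whether that means the patient's or the trial's end; Protocol 15 defines the latter as the last patient's last visit. SAE forms go through the EDC system, so entry into the analysis data is possible but not explicit. This limits the point to events that can be counted.

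**Extension.** A reader might also infer that placebo completers move to Praluent in large numbers. The SAP only names the extension. Lawful commercial use after the visit is enough for the gap to exist, but not to size it.

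**Primary endpoint.** It might be inferred that SWM scores are contaminated. The last scheduled CANTAB test is at the week 96 visit, to which the ban still extends, so truncating the MMRM data would add essentially nothing.

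**Mitigation.** SAP 4.7.1 splits treatment (to +21 days, day 680) from residual treatment (days 681–729), so 49 of the 56 days are residual. SAP 5.7 promises summaries by period and SAP 5.7.1 lists serious TEAEs by patient; safety is descriptive throughout. This helps a reader trace a case, but a residual-period event would still carry the placebo label, and SAP 4.7.1.3 counts every TEAE-period death as on-treatment.

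**Conclusion.** The gap is real and minor. Followed as written, the TEAE rule can assign to placebo a serious event or death that occurs after a placebo patient has started active drug, and it adds that time to placebo patient-years and Kaplan-Meier follow-up.

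The exposed time is firm for an on-schedule completer: 56 days, with all SAEs reportable for the first 30 and deaths throughout. The number of events affected is not. It depends on the extension's drug, start date and uptake, on commercial use after the last visit, and on whether post-visit reports enter the analysis database; the documents settle none of these. The illustrative counts rest on assumed uptake and rates, and their upper ends require every placebo completer to start at day 673. The likely effect is small. The conclusion does not extend to non-serious events or to the primary noninferiority test.

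**What to change.** In SAP 4.7.1, for both arms, end the TEAE period at the earlier of (a) last double-blind injection + 70 days and (b) the day before the first open-label extension dose or the first recorded non-study PCSK9 inhibitor. Use that date for TEAEs, on-treatment deaths, patient-years and Kaplan-Meier censoring, and list later events separately with the drug started and its date. For a completer who starts on day 674, the day after the visit, the period ends on day 673 and 56 days leave it.

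The cost is modest. A few events and days move to a listing. Extension first-dose dates must be merged from the extension study. Commercial starts after the last visit will be known only where recorded, for example on the SAE report: Protocol 5.7 treats medication as concomitant only to the end of the study and no later contact is scheduled, although SAP 4.3 defines concomitant medication through last dose + 70 days. The SAP should state this limit. Visits, dosing, sample size and the primary hypothesis do not change.

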4.7.1.1. Adverse Events and Serious Adverse Events

Adverse events (including serious adverse events (SAE), AEs causing permanent treatment discontinuation, deaths, and AEs of special interest) are recorded from the time of signed informed consent until the end of study. All AEs diagnosed by the Investigator will be reported and described.

All AEs will be dictionary coded by “lowest level term (LLT)”, “preferred term (PT)”, “high level term (HLT)”, “high level group term (HLGT)” and associated primary “system organ class (SOC)” using the version of MedDRA in effect at the time of database lock for the analysis.

Adverse Event Observation Period

- Pre-treatment AEs are AEs that developed or worsened or became serious during the pre-treatment period.
- Treatment-emergent adverse events (TEAEs) are AEs that developed or worsened or became serious during the TEAE period.
- Post-treatment AEs are AEs that developed or worsened or became serious during the post-treatment period.

4.7.1.2. Adverse Events of Special Interest

Adverse events of special interest (AESI) are AEs (serious or non-serious) required to be monitored, documented, and managed in a pre-specified manner as described in the protocol.

In this study, AESI are the following (their complete descriptions are provided in the protocol):

- Local injection site reactions, selected using an e-CRF specific tick box on the AE page;
- Allergic events:
- General allergic events will be tabulated. Events will be selected using standardized MedDRA query (SMQ) “hypersensitivity” (broad and narrow) excluding the preferred terms linked to local injection site reactions (i.e. preferred terms containing “injection site” or “infusion site”)
- ALT ≥ 3 ULN in the case baseline ALT < ULN or ALT ≥ 2 times the baseline value in the case baseline ALT \geq ULN, selected using laboratory data;
- Neurologic events selected using SMQs “demyelination” (broad and narrow), “peripheral neuropathy” (broad and narrow), and “Guillain-Barre syndrome” (broad and narrow) excluding the following preferred terms: “acute respiratory distress syndrome”, “asthenia”, “respiratory arrest” and “respiratory failure” and including selected PTs from SMQ “optic nerve disorders” (see Appendix 10.5, [Table 3](#) for the list of terms)
- Symptomatic overdose with investigational medicine product, selected using HLT “Overdose” and the tick box “Symptomatic Overdose” in the e-CRF AE page.
- Pregnancy of female patient/subject (including male subject’s partner), selected using appropriate MedDRA codes.
- Neurocognitive events:
 - Selected using a company MedDRA query (CMQ), based on the following 5 HLTGs: “deliria (including confusion)”, “cognitive and attention disorders and disturbances”, “dementia and amnestic conditions”, “disturbances in thinking and perception”, and “mental impairment disorders”.
 - A second grouping of terms for neurocognitive events was defined based on Regulatory Agency request (FDA CMQ) (see Appendix 10.5, [Table 4](#) for the list of terms)
- Cataract using HLT “Cataract conditions”
- New onset of diabetes (NOD) will be assessed in patients without diabète at baseline: The definition of new onset of diabetes (NOD) will be the following:
 - Type 1 or type 2 diabetes TEAE (grouping of Medical Dictionary for Regulatory Activities [MedDRA®] terms in Appendix 10.4, [Table 7](#))

and/or

- At least 2 values of HbA1c $\geq 6.5\%$ during the TEAE period

NOTE: For patients with only a single measurement available during the TEAE period, a single value $\geq 6.5\%$ will be considered and qualify the patient as NOD by default.

For patients with several HbA1c measurements but only with the last one $\geq 6.5\%$, this single value $\geq 6.5\%$ will be considered and qualify the patient as NOD by default

and/or

- At least 2 values of fasting plasma glucose (FPG) ≥ 126 mg/dL (7.0 mmol/L)

NOTE: For patients with only a single measurement available during the TEAE period, a single value ≥ 126 mg/dL (7.0 mmol/L) will NOT be considered and will NOT qualify the patient as NOD

For patients with several FPG measurements but only with the last one ≥ 126 mg/dL (7.0 mmol/L), this single value ≥ 126 mg/dL (7.0 mmol/L) will NOT be considered and will NOT qualify the patient as NOD

Analyses of NOD events will also be provided using the tick box on the e-CRF AE page as an exploratory approach in patients without Diabète at baseline.

In addition, the following grouping of events will be provided:

- Hepatic disorder events using SMQ “Hepatic disorder”
- Diabetes mellitus or diabetic complications using 1/ the HLGT “diabetes complications” (including PTs pertaining to the secondary SOC included in the HLGT), 2/ the HLT “diabetes mellitus”, 3/ the HLT “carbohydrate tolerance analyses (incl diabetes)” excluding PTs “blood glucose decreased” and “Glycosylated haemoglobin decreased” and 4/ from the HLT “Hyperglycaemic conditions NEC” only the following PTs “hyperglycaemia”, “Hyperglycaemic unconsciousness” and “Hyperglycaemic seizure”

Neurocognitive Events of Special Interest

Neurocognitive events are defined in this study as AESI, specifically, neurocognitive AEs (serious or nonserious) required to be monitored, documented, and managed in a pre-specified manner as described in this protocol. The neurocognitive events will be adjudicated by the neurocognitive events review committee which is composed of experts in the field of cognition, independent from the sponsor and the investigators. This committee will be responsible for defining, validating, and classifying (in a blinded fashion) AEs of interest possibly related to cognition impairment. A charter and an operational manual will specify the procedures and criteria used for review of these events.

The committee will adjudicate whether a neurocognitive event identified by investigator or the CMQs is indeed a neurocognitive event (Yes/No).

The committee will also adjudicate whether possible etiology of the neurocognitive event is identified.

- Yes: means that there is a clear alternative explanation for the neurocognitive event.
- No: means that there is no clear alternative explanation for the neurocognitive event, and it might be study related.

